FIBER SUPPLEMENTATION IN CHILDREN WITH PEANUT ALLERGY ON ORAL IMMUNOTHERAPY: A RANDOMIZED CONTROLLED PILOT STUDY

Principal Investigator: [name] MD MSc
Department of Pediatrics
[name]
[name]
[contact]

Funding: DFI Multidisciplinary Grant

Study Product: Fiber supplement (Resistant Potato Starch)
(GRAS)

Protocol Number: IRB21-0589

IND Number: N/A

Initial version: March 8, 2021
Amended: August 30, 2021
Amended: September 18, 2021
Amended: October 6, 2021
Amended: October 11, 2021
Amended: October 19, 2021
Amended: June 21, 2022
Amended: May 16, 2023
Amended: August 17, 2023

List of Abbreviations

ACT	asthma control test
AE	adverse event
CBC	complete blood count
CRF	case report forms
DBPCFC	double blind placebo controlled food challenge
FS	fiber supplement
GALT	gut associated lymphoid tissue
GI	gastrointestinal
GRAS	generally regarded as safe
OIT	oral immunotherapy
PI	principal investigator
POIT	peanut oral immunotherapy
RPS	resistant potato starch
RMS	resistant maize starch
ACS	accessible corn starch
SAE	serious adverse event
SCFA	short chain fatty acids
UChicago	The University of Chicago

CONFIDENTIAL

This material is the property of the University of Chicago.
Do not disclose or use except as authorized in writing by the study PI

05.16.2023

Study Summary

Title	Fiber Supplementation in Children with Peanut Allergy on Oral Immunotherapy: A Randomized Controlled Pilot Study.
Short Title	Pinpoint Study
Protocol Number	UCM001
Methodology	Double Blind, Placebo Controlled Pilot Study
Study Duration	July 2021-June 2026 (estimated)
Study Center(s)	UChicago Medicine Comer Children's Hospital UChicago Medicine Comer Children's Merrillville UChicago Medicine South Loop
Primary Endpoints	
 To determine the proportion of subjects who tolerate at least 1043 mg cumulative of peanut protein with no more than mild symptoms at the 12-month DBPCFC
Secondary Endpoints	
 To determine the proportion of subjects who experience dose related GI side effects during oral immunotherapy To determine the proportion of subjects who experience hypersensitivity reactions (other than GI) during oral immunotherapy
Exploratory Endpoints	
 To demonstrate the effect of resistant potato starch (RPS) on the fecal microbiome and metabolome To determine if gnotobiotic mice colonized with the fecal microbiota of study participants models clinical response To evaluate the immunological effects of fiber supplementation in children 
 Change in peanut specific IgE and IgG4 levels Change in peanut skin prick test mean wheal diameter Change in peanut component levels
Number of Subjects	30 peanut allergic subjects will be randomized 1:1 of dietary supplementation of a fiber supplement (RPS) versus placebo
Diagnosis and Main Inclusion Criteria	
 Age 4 to 17 (inclusive) A convincing clinical history of peanut allergy Immune markers consistent with peanut allergy 
 Serum IgE to peanut of >0.35 kUA/L and a skin prick test to peanut >8mm greater than the negative saline control –or– Serum IgE to peanut of >5 kUA/L and a mean peanut wheal diameter on skin prick test 3 to 8mm greater than the negative saline control –or– Serum IgE to peanut of >14 kUA/L and mean peanut wheal diameter on skin prick test 3mm greater than the negative saline control Experience dose-limiting symptoms at or before 100mg challenge dose of peanut protein on screening double blind placebo-controlled food challenge (DBPCFC) Written informed consent from parent/guardian Written assent from subjects above the ages 4-17

Exclusion criteria	
 • History of a chronic disease (other than asthma, allergic rhinitis, and atopic dermatitis) that is at significant risk of becoming unstable or requiring a change in chronic therapeutic regimen • History of mast cell disease • History of recurrent idiopathic or virally induced urticaria, angioedema or anaphylaxis • Any history or presence of autoimmune, cardiovascular disease, chronic lung disease (other than asthma), malignancy, psychiatric illness, or gastrointestinal inflammatory conditions, including celiac disease, inflammatory bowel disease, eosinophilic esophagitis or other eosinophilic gastrointestinal disease • Current participation in any other interventional study • Subject who has undergone any type of oral immunotherapy • Severe asthma or uncontrolled mild to moderate asthma • Uncontrolled atopic dermatitis • Current use of oral steroid medications • Use of >1 bursts of oral steroid medications in the past year • Inability to eat by mouth the fiber supplementation or placebo control and peanut flour for any reason • Use of any therapeutic antibody (biologic medication) or any immunomodulatory medication in the past 12 month (other than a short course of oral steroids) • Current use of any type of immunotherapy • Pregnancy or lactation • Allergy to potato, corn, oat or cow's milk • Unwillingness to carry an epinephrine autoinjector • Unwillingness to comply with activity restrictions during OIT or any other study procedure
Study Product and Planned Use	A prebiotic, resistant potato starch (RPS), will be given as a dietary supplement before and during oral immunotherapy to peanut
Reference therapy	Oral immunotherapy to peanut
Treatment Description	Subjects who meet inclusion criteria will be randomized 1:1 to receive either RPS or placebo. After 30 days of prebiotic therapy, subjects will start peanut oral immunotherapy (POIT) in addition to the prebiotic and continue through a prescribed course of POIT, approximately 180 days. After completion of POIT up dosing, subjects will continue on maintenance POIT plus prebiotic therapy for an additional 180 days at which time they will undergo a DBPCFC. Subjects will then stop prebiotic therapy and continue on maintenance POIT in extended observation for approximately 4 years.

CONFIDENTIAL


Schedule of Events
	
 • Inclusion/exclusion criteria • Informed consent (and assent, as age appropriate) • Medical/allergy history • Concomitant medications • Physical examination, including height and weight • Vital signs • Quality of life assessment • Spirometry (if has asthma diagnosis as COVID allows) • eNO (if has asthma diagnosis as COVID allows) • Asthma control test (ACT; if has asthma diagnosis) • Blood draw (total IgE, peanut-specific IgE, peanut component testing, peanut-specific IgG4, complete blood counts (CBC), 25-hydroxyvitamin D (screening only), omega-3 index (screening only)) • Skin prick testing (screening and exit) • Stool collection • DBPCFC (screening and exit) • Randomization • Study product administration and dispensation for home dosing • Peanut oral immunotherapy (POIT) -in both placebo/control and investigational groups. • Dose compliance monitoring • Adverse event (AE) monitoring (including serious adverse event)

Statistical Methodology
	
Chi-square testing (or non-parametric equivalent) will be used to compare categorical variables. Student's t-test (or non-parametric equivalent) will be used to compare continuous variables. Microbial relationships between samples will be compared using principal coordinate analysis and average-neighbor hierarchical clustering. Welch's t-test will be used to determine significant abundance differences between OTUs.

CONFIDENTIAL

1 Introduction

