As a result of this hypothesis, interest has been gained in manipulating the microbiome of the GI tract in order to control chronic, non-infectious inflammatory diseases, such as peanut allergy. Prebiotic, probiotic and postbiotic formulations may all hold therapeutic potential. In this trial, we propose using a prebiotic therapy (potato starch) previously shown to modulate the microbiome in adults in children with peanut allergy to determine if it has an effect on the commensal bacteria of the GI tract and subsequently influences the immune response.¹²

Murine model studies have demonstrated that both germ free mice and mice treated with a cocktail of antibiotics, beginning pre-weaning, are highly susceptible to allergic sensitization to food¹⁰. Studies involving selective colonization of gnotobiotic mice demonstrate that mucosa-associated Firmicutes in the Clostridia class protect against allergic sensitization by inducing IL-22 dependent barrier protective responses in the intestine that limit systemic access of allergenic food proteins^{10,12}. Numerically, Firmicutes (which includes Clostridia) are a dominant component of the gut microbiota^{13,14}. Many Clostridia are involved in the complex process of digesting fiber and resistant starches. This process involves sequential breakdown by particular bacterial taxa and ultimately results in the formation of short chain fatty acids (SCFAs). SCFAs have potent immunomodulatory effects correlated with host health^{15,16} including induction of colonic regulatory T cells and improvement of allergy symptoms in a mouse model^{17,18}. Butyrate, in particular, is an important energy source for colonic epithelial cells¹⁹. Butyrate drives oxygen consumption by colonocytes through β -oxidation, which maintains a locally hypoxic niche for butyrate-producing obligate anaerobes²⁰. Induction of SCFA production may therefore be a key component of Clostridia's allergy-protective effect.

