Spirometry	X	X	X	X				X	X
sNO	X								
ACT Score	X								
Skin Prick Test	X			X				X	
Blood Draw	X			X				X	
Stool Sample Collection		X		X		X (monthly)	X	X	
DBPCFC Randomization		X						X	
DBPCFC Administration		X	X					X	X
Study Arm Randomization			X						
Prebiotic Dispensing/Placebo 7.15 grams			X						
Dosing/AE Log Collection				X		X	X		
SOC Consent for POIT				X					
POIT Initial Escalation				X					
OIT Administration					X	X			

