3.3 Secondary Study Endpoints

The secondary endpoints are as follows:

- To determine the proportion of subjects who experience dose related GI side effects during oral immunotherapy

CONFIDENTIAL

This material is the property of the University of Chicago.
Do not disclose or use except as authorized in writing by the study PI

05.16.2023

- To determine the proportion of subjects who experience hypersensitivity reactions (other than GI) during oral immunotherapy

The exploratory endpoints are as follows:

- To demonstrate the effect of resistant potato starch (RPS) on the fecal microbiome and metabolome
- To determine if gnotobiotic mice colonized with the fecal microbiota of study participants models clinical response
- To evaluate the immunological effects of fiber supplementation in children
 - Change in peanut specific IgE and IgG4 levels
 - Change in peanut skin prick test mean wheal diameter
 - Change in peanut component levels

4 Subject Selection and Withdrawal

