6.3 Visit 4 (30 days after visit 3)

- Interval medical history
- Vital signs
- Physical examination, including height and weight
- Spirometry (if has asthma diagnosis as COVID allows)
- Skin prick testing
- Blood draw
- Stool sample collection
- Collection of dose and symptom logs
- Standard of care consent for POIT
- POIT initial dose escalation day

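### The synopsis and the schedule disagree on skin prick testing at Visit 4, and no immune endpoint names its visit, so the contrast of fiber without POIT is not prespecified

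*Combined protocol and SAP*

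**What the plan says.** On the timing of the skin test, the Combined protocol and SAP gives two answers.

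- Study Summary, Schedule of Events: "Skin prick testing (screening and exit".
- Section 3.1, Schedule of Procedures: the row "Skin Prick Test" is marked at V1, V4 and V16, as far as the column positions can be read. Section 6.3, headed "Visit 4 (30 days after visit 3", lists "Skin prick testing" with blood and stool, above the POIT escalation line. Section 6.7 lists the test at Visit 16.

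The same synopsis cell sets no visit limit on the peanut serology: "Blood draw (total IgE, peanut-specific IgE, peanut component testing, peanut-specific IgG4, complete blood counts (CBC), 25-hydroxyvitamin D (screening only". The schedule and section 6.3 both include blood at Visit 4.

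The exploratory aim is "To evaluate the immunological effects of fiber supplementation in children". Its measures are changes, for example "Change in peanut skin prick test mean wheal diameter" in section 3.3, and none has a baseline or outcome visit. Section 2.2 makes immune markers a secondary objective. Section 7.2 compares continuous variables by Student's t-test or a non-parametric equivalent, with no time point and no baseline adjustment.

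**The concern.** The rationale in section 1.1 is sequential. The supplement is given "to determine if it has an effect on the commensal bacteria of the GI tract and subsequently influences the immune response". Randomization and dispensing are at V3, and POIT begins at V4, so V4 is the only immune assessment after randomization at which the arms differ by fiber and POIT has not yet acted. By V16, at month 14, both arms have been scheduled for a long course of daily peanut, which section 1.1 says continues to change the immune response.

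Two things are at stake. Staff who work from the synopsis would omit the Visit 4 skin test, and once POIT has started it cannot be made up. Also, with immune measures at both V4 and V16 and no visit named, the outcome visit can be chosen after the data are seen.

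**Working it through.** **1. Timing of the skin test.** The synopsis allows screening and exit. The schedule has V1, V4 and V16, and sections 6.3 and 6.7 confirm V4 and V16. The conflict is confined to the skin test at V4. Blood at V4 is consistent throughout, so peanut IgE, IgG4 and components are unaffected.

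**2. What each visit can estimate.** Both arms receive POIT.
- Arm difference at V4: fiber against placebo, without POIT.
- Arm difference at V16: fiber against placebo, on top of POIT.

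Both are randomized comparisons, but of different quantities. The endpoints name neither visit.

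**3. Limits of V4.** From the visit-day row, V1 is D-65, V3 is D-30 and V4 is D1.
- V1 to randomization: 65 − 30 = 35 days.
- V1 to V4: about 35 + 30 = 65 days, of which only the last 30 are on supplement.

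Baseline blood and skin test at V1 precede the screening challenges at V2 and V3, so the V1-to-V4 change includes a peanut challenge. This applies to both arms and does not bias the arm difference, but it can add scatter. V4 is also the initial escalation day. Sampling is listed above escalation, but the order on the day is not stated.

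**4. Precision.** The plan has no figure to reproduce: section 7.1 gives 30 subjects with no alpha, power, SD or dropout. At 1:1 that is 15 per arm. For illustration, assume a common SD at both visits and 10 to 12 per arm at V16. The 95% half-width in SD units is t(0.975, 2n−2) × √(2/n).

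| n per arm | t | √(2/n) | half-width (SD) | relative to 15 |
|---|---|---|---|---|
| 15 | 2.048 | 0.365 | 0.75 | 1.00 |
| 12 | 2.074 | 0.408 | 0.85 | 1.13 |
| 10 | 2.101 | 0.447 | 0.94 | 1.26 |

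The difference detectable with 80% power (two-sided 5%, t-test) is 1.06 SD at 15 per arm, 1.20 at 12 and 1.33 at 10. Even a complete V4 sample can show only a large effect.

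**5. Unequal SDs.** Suppose the SD of log10 change is 0.15 at V4 (n = 15) and 0.4 (n = 12) to 0.6 (n = 10) at V16. The half-widths become 0.15 × 0.75 = 0.11, 0.4 × 0.85 = 0.34 and 0.6 × 0.94 = 0.56 log10, a three- to five-fold gap. That gap comes mostly from the assumed SDs, which the documents do not give.

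**The case against.** A reader might infer four stronger things, and the documents do not support them.

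- *The Visit 4 contrast is lost.* It is not. The detailed schedule collects skin test, blood and stool at V4, the serology is not in conflict, and no endpoint excludes V4.
- *V16 is confounded by POIT.* POIT is given in both arms, so the randomized comparison at V16 holds. Section 1.1 presents RPS as an addition to POIT and section 2.1 concerns POIT outcomes, so the add-on effect is the one mainly intended.
- *V16 immune data are depleted.* Sections 3.1 and 8.4.3 withhold only the exit DBPCFC from children who stop POIT or do not reach six months at 300 mg. They stay under observation. Section 1.1 mentions notable dropout in earlier trials but gives no rate. What stands is that V16 falls under the exit-challenge phase and the plan does not say whether blood and skin test are still taken from these children.
- *V4 is several times more precise.* That rests on assumed SDs. A narrower interval for a different quantity is also not more information about the same effect, and a 30-day effect may be smaller.

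It is also fair to say that these are exploratory endpoints in a 30-child pilot, where failing to name a visit would by itself be a matter of detail. What remains is a contradiction about a procedure that cannot be repeated, together with an analysis that ignores a baseline already collected.

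**Conclusion.** The point holds in a limited form. The synopsis contradicts the schedule and section 6.3 on the skin test at V4, and the passages must be reconciled. No immune endpoint names its visit, and the analysis is an unadjusted two-sample test, although V4 is the only scheduled assessment that can show fiber without POIT. This reading assumes that V4 sampling precedes the first POIT dose, as the list order suggests.

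No advantage in precision can be claimed for V4 beyond the 13% to 26% illustration, which itself assumes equal SDs and 10 to 12 children per arm at V16. V4 supplements V16 and does not replace it. Importance is minor to moderate: the endpoints are exploratory, but they serve a stated secondary objective.

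**What to change.** 1. Make the synopsis agree with the schedule on skin prick testing: V1, V4 and V16.
2. In sections 3.3 and 7.2, specify two exploratory arm contrasts for peanut IgE, IgG4, components and wheal, each adjusted for the V1 value (for example by analysis of covariance). The first is at V4, as fiber alone, in all randomized children with a V4 measure. The second is at V16, as fiber plus POIT. Report estimates with intervals.
3. State whether V4 blood and skin testing precede the first POIT dose.
4. State whether V16 blood and skin testing are obtained in children who have no exit DBPCFC.

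No visit, sample or subject is added beyond the current schedule. The cost is an amendment to the text and at least four further exploratory comparisons, one for each marker group at V4 and more if components are reported singly. They should be labelled exploratory and not read as separate tests of efficacy.

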1.1 Background and Rationale

This document is a protocol for a human research study. This study is to be conducted according to US and international standards of Good Clinical Practice (International Conference on Harmonization ICH E6), the Code of Federal Regulations Title 21 parts 812, and other applicable government regulations and Institutional research policies and procedures.

After a 50% increase in prevalence between 1997 and 2011, food allergy has become one of the most common chronic diseases of childhood now affecting 8% of American children, or roughly 2 children in every classroom in the United States. In a similar time period, the prevalence of peanut allergy has more than tripled in American children.¹ Children with peanut allergy have been shown to have a worse quality of life than children with insulin dependent diabetes mellitus and feel limited in their ability to safely attend social events.² In fact more than 40% of children with peanut allergy have had a severe allergic reaction requiring emergency care at least once in their life, and 20% of children with peanut allergy have a reaction to peanut every year.¹ These reactions are potentially life threatening and lead to significant anxiety and a financial burden for families with peanut allergic children.³ Unfortunately, children rarely grow out of peanut allergy naturally, and although it is a potentially fatal disease, currently, only one FDA approved treatment exists, oral immunotherapy (OIT) for peanut.⁴

Oral immunotherapy is a method of inducing desensitization to peanut in those with an IgE mediated peanut allergy to make them “bite-safe”, or unlikely to experience a severe reaction upon the accidental ingestion on peanut. When undergoing oral immunotherapy, a child is given slowly increasing doses of peanut that are below the threshold of reactivity that eventually induce an increasing threshold, so an even higher dose of peanut can be given safely. After approximately 6 months of up-dosing, children become tolerant to eating one peanut a day. After continuing to eat one peanut a day, desensitized children appear to undergo continued immunomodulation that raises their reactivity threshold to be tolerant of ingestion of 3 peanuts.⁴⁻⁶

Unfortunately, OIT is an imperfect therapy as >70% of children undergoing therapy experience gastrointestinal (GI) side effects, including eosinophilic esophagitis, which has led to a significant drop out rate in clinical trials. In addition, a high rate of systemic allergic reactions, that were treated with epinephrine, have been seen in study populations.⁴ Finally, little evidence exists to support using OIT as a cure for or to induce remission of peanut allergy, nor does evidence exist that supports the ability of children to “free eat” peanut in their diet after completion of therapy. As a result, children must continue to take a daily dose of peanut protein for the rest of their lives in order to remain bite safe without expectation of any other benefit.⁷

One barrier to the development of a more effective therapy is the lack of understanding of the pathogenesis of this disease. The rate of increase in peanut allergy is too high to be explained by genetics alone. A theory that may, however, explain both the development and increasing prevalence of peanut allergy is the “microbiome hypothesis” which posits that commensal microbes or “good bacteria” in our gastrointestinal (GI) tract interact with our immune system through production of short chain fatty acids (SCFA), including butyrate, after digestion of dietary fibers. In turn, butyrate acts as a “postbiotic” that influences both the development and severity of chronic non-infectious inflammatory diseases such as food allergy.⁸⁻¹⁰

This hypothesis is supported by the vast changes in the modern lifestyle that may impact colonization of commensal microbes in our GI tract, including diet, antibiotic use, antiseptic use, food sterilization, smaller family sizes, and reduced exposure to farm animals. The American diet is largely devoid of fibrous fruits and vegetables that act as prebiotic “food” for our commensal bacterial and instead high in processed sugars which favor growth of non-SCFA producing bacterial species. Both antibiotics and external antiseptic use have been shown to influence the GI microbiome, including antibiotics fed to livestock later

CONFIDENTIAL

This material is the property of the University of Chicago.
Do not disclose or use except as authorized in writing by the study PI

05.16.2023

sacrificed for meat. Finally, the colonization or recolonization of commensal bacteria has likely been affected by the lack of exposure to bacteria in our day to day life.¹¹

As a result of this hypothesis, interest has been gained in manipulating the microbiome of the GI tract in order to control chronic, non-infectious inflammatory diseases, such as peanut allergy. Prebiotic, probiotic and postbiotic formulations may all hold therapeutic potential. In this trial, we propose using a prebiotic therapy (potato starch) previously shown to modulate the microbiome in adults in children with peanut allergy to determine if it has an effect on the commensal bacteria of the GI tract and subsequently influences the immune response.¹²

Murine model studies have demonstrated that both germ free mice and mice treated with a cocktail of antibiotics, beginning pre-weaning, are highly susceptible to allergic sensitization to food¹⁰. Studies involving selective colonization of gnotobiotic mice demonstrate that mucosa-associated Firmicutes in the Clostridia class protect against allergic sensitization by inducing IL-22 dependent barrier protective responses in the intestine that limit systemic access of allergenic food proteins^{10,12}. Numerically, Firmicutes (which includes Clostridia) are a dominant component of the gut microbiota^{13,14}. Many Clostridia are involved in the complex process of digesting fiber and resistant starches. This process involves sequential breakdown by particular bacterial taxa and ultimately results in the formation of short chain fatty acids (SCFAs). SCFAs have potent immunomodulatory effects correlated with host health^{15,16} including induction of colonic regulatory T cells and improvement of allergy symptoms in a mouse model^{17,18}. Butyrate, in particular, is an important energy source for colonic epithelial cells¹⁹. Butyrate drives oxygen consumption by colonocytes through β -oxidation, which maintains a locally hypoxic niche for butyrate-producing obligate anaerobes²⁰. Induction of SCFA production may therefore be a key component of Clostridia's allergy-protective effect.

Initial translational studies established that the composition of the fecal microbiota is altered (and butyrate production is reduced) in infants with cow's milk allergy²¹. Feehley et al. demonstrated that there were numerous differentially abundant bacterial operational taxonomic units (OTUs) between healthy and CMA infants or GF mice colonized with the feces of these infants²². Analysis of differentially abundant OTUs that distinguished the CMA and healthy populations in both the human donors and colonized mice. Correlation of ileal taxa with differentially expressed genes in the ileum of healthy-colonized mice identified a Clostridial species, *Anaerostipes caccae*, that mimicked the effects of the healthy microbiota, supporting a causal role for a specific bacterial taxon in protection against food allergy. *A. caccae* is an extremely efficient butyrate producer commonly found in the infant gut but can be identified in adults as well^{23,24}.

More recently, evidence expands this observation beyond infants. Identification of differentially abundant OTUs in healthy and allergic twins revealed that 84% were in the Clostridia class²⁵. These bacterial OTUs were then correlated with fecal metabolites from nonbiased metabolomic profiling, which identified another potentially protective Clostridial species in healthy twins: *R. bromii*. *R. bromii* is measurable in the feces of many (but not all) adults and is recognized as a keystone species for the degradation of type III resistant starches, like resistant potato starch (RPS)²⁶. *R. bromii* abundance in feces significantly increases upon dietary intervention with RPS^{27,28}. Individuals that do not have detectable *R. bromii* in the feces before beginning a RPS-supplemented diet consume about 40% less total starch than individuals colonized with *R. bromii*, demonstrating that this species alone is responsible for much of the total starch digestion in the colon²⁷. *R. bromii* performs the initial phases of resistant starch digestion, producing intermediate metabolites such as acetate which can then be consumed by butyrate producing bacteria. While *R. bromii* is not capable of producing butyrate itself, a recent report demonstrated that two weeks of RPS consumption by young adults was sufficient to induce detectable increases of butyrate in feces²⁹. This increase in butyrate concentration was greater in individuals who also demonstrated increased fecal abundance of *R. bromii* compared to those with no change. Butyrate concentration was also significantly correlated with changes in the abundance of *Eubacterium rectale*, a well characterized butyrate producing Clostridia²⁹. Interestingly *E. rectale* is one of the few bacterial species detectable in the microbiomes of most healthy individuals worldwide³⁰. Taken together the data suggest that *R. bromii* is a tractable biomarker, associated with a healthy microbiota and increased butyrate production, and responsive to dietary intervention. Interestingly, and in agreement with our hypothesis, the Canadian

CONFIDENTIAL

Healthy Infant Longitudinal Development birth cohort study reported that depletion of *R. bromii* early in life (3 and 12 months of age) is associated with the development of atopy and reduced genetic potential to produce butyrate³¹.

Due to the existing limitations of OIT, multiple strategies of combination therapy to reduce symptoms associated with treatment and induce remission or prolonged non-responsiveness have been trialed, but each have significant limitations thus far. Combining the IgE-blocking antibody omalizumab with peanut OIT reduces adverse reactions initially, but these adverse events return after stopping omalizumab treatment and to date the cost associated with omalizumab has limited its utility in the clinical setting³². Microbial therapies have also recently been studied in combination with OIT in both preclinical and clinical settings³³. Both prebiotics (bacteria-accessible carbohydrates) and probiotics (live bacteria themselves) can improve allergic responses to food in mouse models^{16,33,34}. Further, the combination therapy of OIT plus *Lactobacillus rhamnosus* GG (LGG), a bacterial species that when supplemented in infant formula increases the abundance of butyrate-producing bacteria in feces, demonstrated improved efficacy of OIT compared to previous studies and showed potential for inducing remission at 2-5 weeks and up to four years after discontinuing treatment^{21,35,36}. However, this study lacked appropriate controls preventing adoption of the approach.

In a series of publications, the beneficial effects of both the Clostridia class (as a whole) as well as individual species (*A. caccae* and *R. bromii*) has been shown in protection against food allergy in humans and gnotobiotic mice. The candidate species that we have identified may work together in the process of fiber digestion to produce butyrate. As mentioned above, others have shown that a significant expansion of *R. bromii* upon dietary supplementation with RPS correlates with increased concentrations of fecal butyrate^{28,29}. We now seek to extend these findings by using RPS as an additive therapy for peanut allergic children undergoing POIT. We predict that the high incidence of GI symptoms and systemic allergic reactions during POIT may be due, in part, to the fact that POIT is administered without any strategy to address intestinal barrier dysfunction in allergic subjects. We predict that administering RPS prior to and during POIT will expand populations of protective bacteria, elicit a bacteria-induced barrier protective response, and improve clinical outcomes of POIT.

